1. INTRODUCTION

Background

Uncomplicated, non-purulent cellulitis is an infection describing the subcutaneous tissue of the skin.¹ Group A streptococcus (*Streptococcus pyogenes*), β -hemolytic streptococci and methicillin-susceptible *Staphylococcus aureus* are the most common causative agents for non-purulent cellulitis. Patients typically present to the emergency department (ED) with pain, redness, swelling and induration of the affected skin. The borders of the reddened affected skin are irregular and patchy in patients with cellulitis. A minority of patients may exhibit signs of systemic illness, such as fever or tachycardia. The diagnosis of non-purulent cellulitis is clinical. Once the diagnosis is made, emergency physicians are expected to select appropriate antibiotic therapy. The physician must select the appropriate route (oral versus intravenous), agent, dose frequency and duration.

Burden of Disease

Cellulitis is a common condition diagnosed and managed in the ED and carries significant financial burden on healthcare systems globally. Extrapolating from US data², there are approximately 193,000 Canadian ED visits per year for cellulitis. Although Canadian data are lacking, a single Vancouver ED diagnosed 2234 patients with skin and soft tissue infections from 2003 to 2004, representing 2% of all ED visits.³ A 2011 report by the Canadian Institute for Health Information found that cellulitis was the 5th most common reason for an ED visit in patients aged 45 to 64 years.⁴ Cellulitis is responsible for a significant healthcare system burden due to hospital admission and subsequent costs. We conducted a health records review at The Ottawa Hospital Civic and General campuses, and found that 29.6% of all ED patients with non-purulent cellulitis are admitted to hospital.⁵ A study in the United States reported an average cost of \$8023 USD for hospitalized patients with skin and soft tissue infections with a mean length of stay of 4.9 days.⁶

Current Guidelines

Owing to a lack of high-quality evidence, published empiric treatment guidelines are largely based on expert opinion.⁷⁻¹⁰ There are currently no Canadian guidelines for the management of skin and soft tissue infections. Despite the increasing burden of this common presentation, current evidence is lacking regarding the optimal management of cellulitis.

Oral Antibiotic Therapy: Cephalexin

The majority of ED patients with non-purulent cellulitis are treated with oral antibiotics and discharged home. Oral antibiotic therapy holds several advantages over the intravenous route, including lower risk of complications, decreased cost, and increased patient convenience and comfort.^{11,12} We conducted a national survey of 391 emergency physicians, which revealed that the majority (89%) prescribed cephalexin as first-line oral antibiotic therapy for a duration of seven days to treat patients with non-purulent cellulitis.¹³ The currently recommended dose range of cephalexin is 250mg to 1000mg QID (i.e. four times daily).¹⁴ Infectious Disease Society of America guidelines for treatment of skin and soft tissue infections recommend cephalexin 500mg QID for a minimum of five days.⁷ However, high-dose cephalexin (1000mg) achieves a higher peak serum concentration than standard-dose cephalexin (500mg), and reaches serum

concentrations that are comparable to parenterally (i.e. intravenous or intramuscular) administered cephalosporins.^{15,16} Owing to its short serum elimination half-life (≤ 1 hour), cephalexin must be administered up to four times daily irrespective of the dose used.¹⁶ With higher peak serum concentrations, administering high-dose cephalexin may lead to a reduction in treatment failures for patients with non-purulent cellulitis. Locally, infectious disease specialists in Ottawa recommend the use of high-dose cephalexin, but this is not based on high-quality evidence. There are no published studies evaluating whether high-dose cephalexin (1000mg QID) is superior to standard-dose (500mg QID) cephalexin.

Oral Antibiotic Treatment Failure

The oral antibiotic treatment failure rate in Canadian EDs is approximately 20%.^{5,17,18} If an oral antibiotic treatment failure occurs, patients are typically switched to intravenous therapy and may require hospitalization. Intravenous therapy has many disadvantages, including patient inconvenience, patient discomfort, the added risk of intravenous line complications and higher cost. The current high oral antibiotic treatment failure rate may be due to suboptimal dosing of first-line oral therapy. We hypothesize that high-dose cephalexin may lead to **lower rates of treatment failure** and subsequently **improved patient outcomes** (fewer hospitalizations and avoidance of intravenous antibiotic complications).

2. RATIONALE

Before embarking on a large, multicenter trial, it is essential to conduct a smaller pilot to test and refine study procedures and demonstrate that it is feasible to proceed with a multicentre trial.

3. RESEARCH QUESTION & OBJECTIVES

The **ultimate goals** of this research are to reduce antibiotic treatment failure, return ED visits and use of outpatient intravenous antibiotics. The **specific goals** of this double-blind pilot randomized controlled trial are to (1) establish feasibility and refine study procedures before embarking on a larger, fully powered multicenter trial; and (2) generate preliminary evidence of effectiveness comparing high-dose to standard-dose cephalexin for non-purulent cellulitis.

Our **specific** objectives are to:

1. Measure feasibility outcomes, including recruitment rate, success of blinding and adherence; and
2. Measure patient outcomes, including oral antibiotic treatment failure rate and frequency of adverse events

4. METHODS

4.1 Design and Setting

We will conduct a parallel arm double-blind randomized controlled pilot trial at the Civic and General campus emergency departments (EDs) of The Ottawa Hospital. The study will operate seven days a week from 0800 to 2000, and will be conducted over a 6-month timeframe.

4.2 Study Population

4.2.1 Inclusion Criteria

Adults (age ≥ 18 years) with non-purulent cellulitis determined by the treating emergency physician to be eligible for outpatient care with oral antibiotics.

4.2.2 Exclusion Criteria

- a) Age < 18 years
- b) Patient already taking oral antibiotics
- c) Treating physician decides that intravenous therapy is required
- d) Abscess requiring an incision and drainage or needle aspiration procedure
- e) Known prior cellulitis secondary to methicillin-resistant *Staphylococcus aureus*
- f) Cellulitis secondary to a human or animal bite wound
- g) Surgical site infection
- h) Malignancy and currently being treated with chemotherapy
- i) Febrile neutropenia (temperature $\geq 38^{\circ}\text{C}$ plus absolute neutrophil count < 500 cells/ μL)
- j) Solid organ or bone marrow transplant recipient
- k) Renal impairment with creatinine clearance < 30 mL/min
- l) Pregnant or breastfeeding
- m) Allergy to cephalosporins or history of anaphylaxis to penicillin
- n) Inability to provide consent

4.3 Orientation to Study

The following will be used to orient and educate ED staff to the study: i) research team to individually orient all emergency physicians and residents; ii) oral presentation at grand rounds; iii) periodic email; and iv) posters in ED physician work areas.

4.4 Patient Selection

A trained research assistant (RA) will identify potentially eligible patients during weekday business hours, and will be available on-call for after hours. The RA will approach the treating physician to discuss enrolling eligible patients. After confirming patient eligibility, the RA will explain the study details to the patient and obtain verbal informed consent. In addition, the RA will screen the ED patient log to identify missed patients.

4.5 Ethical Considerations

Ethical approval for the proposed study will be sought from the Ottawa Health Science Network Research Ethics Board (OHSN-REB). As both high-dose and standard-dose cephalexin are currently used in practice, we do not perceive any risks to patients or any ethical challenges in conducting this study.

4.6 Intervention and Comparator

The intervention is high-dose cephalexin (1000mg PO QID) for seven days. The comparator is standard-dose cephalexin (500mg PO QID) plus oral placebo for seven days. The duration of

therapy was chosen based on a national survey of the Canadian Association of Emergency Physicians.¹³

4.7 Allocation Concealment and Blinding

Eligible patients will be randomized (1:1) to high-dose versus standard-dose arms. The randomization sequence will be computer-generated by a statistician from the Ottawa Methods Center (OMC) using a randomly permuted block design with randomly varying lengths of 4 or 6. Allocations will be stratified by cellulitis location (lower limb vs. other). The research assistant will log into a secure web-based system managed by the OMC to determine the allocation for each patient who has consented and been enrolled. Cephalexin and placebo tablets will be encased in identical capsules, prepared and packaged independently by The Ottawa Hospital Pharmacy. The research assistant will verify the correct package for an enrolled patient with the ED nurse. The ED nurse will then dispense the study medications. The patients, treating physician and research team will be blinded.

4.8 Outcomes

Our pilot trial has both **feasibility** and (preliminary) **effectiveness** outcomes.

4.8.1 Feasibility Outcomes

The **primary feasibility outcome** is:

1. Patient recruitment rate (percentage of approached eligible patients who are successfully recruited) over 6 months. Our goal is to recruit at least 29% of eligible patients (see Sample Size)

The secondary feasibility outcomes are:

2. Ability to approach eligible patients (goal <10% missed)
3. Ability to blind patients using a questionnaire
4. Protocol adherence (i.e. fully adherent to allocated treatment for 7 days)
5. Loss to follow up at 14 days (goal <10% attrition)

4.8.2 Effectiveness Outcomes

The **primary effectiveness outcome** is:

1. **Oral antibiotic treatment failure**, defined as a change in antibiotic (change in class of oral antibiotic or step up to intravenous therapy) within 7 days due to worsening infection, which is defined as:
 - a. New fever (temperature $\geq 38.0^{\circ}\text{C}$) or *persistent* fever at Day 3 follow up; or
 - b. Increasing area of erythema $\geq 20\%$ from baseline; or
 - c. Increasing pain ≥ 2 points from baseline (numeric rating scale)

The secondary effectiveness outcomes are:

2. Clinical cure (no erythema, pain and fever) at day 7
3. Clinical response ($\geq 20\%$ reduction in area of erythema compared to baseline) at day 3
4. Adverse events (e.g. vomiting, diarrhea, rash) at 14-day telephone follow-up
5. Unplanned i) return ED visits; and ii) hospitalization at 14-day telephone follow-up

Baseline clinical data will be recorded at the index ED visit. Patients will be assessed at a home visit by the research assistant on: 1) Day 3 (mid-therapy); and 2) Day 7 (end-of-therapy). If criteria are met for worsening infection, they will be sent to the ED for evaluation. If a home visit is not possible, the following alternate methods of follow up will be offered to patients:

1. Video follow up via a mobile device (tablet or phone) using FaceTime, Zoom or Skype. The patient must own a mobile device with one of these applications in order to proceed with this option. If this option is chosen, the patient will be given a disposable tape measure and disposable temperature strip so that they can measure the dimensions of erythema and temperature, respectively during the video follow up. The patient will be asked to download a free mobile application (Preventicus Heartbeats; <https://www.preventicus.com/en/>) that will allow the patient to measure their heart rate at the time of follow up.
2. Return to the ED for assessment. In this case, hospital parking fees will be reimbursed for the patient

Study participants will complete a questionnaire on Day 7 regarding effectiveness of blinding, medication adherence and adverse events.

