6.2 Informed Consent

The emergency physician will inform the patient about the study (i.e. we are assessing two different approved doses of the most commonly used antibiotic for cellulitis) and will ask for permission to allow a research assistant to speak with the patient about the study. If permission is granted, the emergency physician will delegate the task of obtaining oral consent (i.e. structured script read to the patient and ability to answer any questions the patient may have) using the integrated consent model to the research assistant. The integrated consent model has been chosen as the two treatment doses being evaluated are currently used in practice by doctors when treating cellulitis. The approved dosing range for cephalexin is 1g to 4g daily. Therefore, we anticipate minimal risk to patients who decide to participate in the trial, and the integrated verbal consent approach allows for a robust and practical approach to the consent process in the Emergency Department setting.

The research assistant will be trained to obtain oral consent using an OHSN-REB approved script. Once the discussion is complete, the research assistant will document the discussion and patient decision on the study page under the research section of the Epic electronic health record. The patient will be provided with an information sheet that includes study information. The informed consent script and patient information sheet are uploaded separately within the OHSN-REB application.

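### The failure definition leaves out same-class oral switches, dose changes and longer courses given for worsening, which can distort the preliminary failure rates in a comparison of two doses of one drug

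*Combined protocol and SAP*

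**What the plan says.** Section 4.8.2 builds the primary effectiveness outcome from two parts, and both are required. The first is an antibiotic change, limited by a parenthesis to a "change in class of oral antibiotic or step up to intravenous therapy". The second is timing and cause: "within 7 days due to worsening infection", where worsening means new or persistent fever, "Increasing area of erythema" of at least 20%, or a pain rise of at least 2 points. Worsening without a qualifying change is not failure.

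For patients who worsen, the same section says "If criteria are met for worsening infection, they will be sent to the ED for evaluation". It does not say which treatment changes may follow or how other changes are classified.

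Section 4.6 sets the arms: "The intervention is high-dose cephalexin (1000mg PO QID) for seven days" and "The comparator is standard-dose cephalexin (500mg PO QID) plus oral placebo for seven days". Section 6.2 adds that "The approved dosing range for cephalexin is 1g to 4g daily". Section 1 notes that "infectious disease specialists in Ottawa recommend the use of high-dose cephalexin", and also that intravenous treatment is the usual next step after oral failure. Section 4.7 blinds patients, treating physicians and the research team. Appendix A, part D, bases the definition on a systematic review and gives no reason for leaving out same-class or same-drug changes.

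**The concern.** Three responses to documented worsening fall outside the definition: a switch to another oral drug of the same class, a higher dose of cephalexin, and a longer course. How an added oral drug would be classified is not stated.

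In many antibiotic trials this would be a minor matter of wording. Here the randomised contrast is itself a dose of one drug, so a dose increase after worsening bears directly on the question. A standard-dose patient moved to the higher dose for worsening would be receiving the other arm's regimen, yet would be recorded as a standard-dose non-failure under the intention-to-treat analysis in section 4.12.

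At stake are the preliminary failure rates and their difference, and the soundness of the endpoint if it is carried into the full-scale trial. The primary feasibility outcome is not affected.

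**Working it through.** **1. Does any other section bring these patients back?** No. Section 4.12 gives the analysis of the outcome without redefining it, and Appendix A, part D, gives only its origin. Any intravenous step counts, whatever the class, so the gap concerns oral changes only. An extension decided after Day 7 is also outside the time window.

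**2. The one stated figure that rests on this endpoint.** Appendix A, part A, gives a total of 2552 for 20% failure, a 5-point difference and 90% power. Alpha, the allocation ratio and the dropout allowance are not stated there. I assume two-sided 0.05, 1:1 allocation and a reduction from 20% to 15%. With p̄ = (0.20 + 0.15)/2 = 0.175:

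n per arm = [1.960·√(2·0.175·0.825) + 1.282·√(0.20·0.80 + 0.15·0.85)]² / 0.05² = (1.053 + 0.687)² / 0.0025, which is 1212 after rounding up (unrounded inputs). The total is 2424.

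2424/0.95 = 2552, so the stated total matches if 5% dropout was allowed for. With a continuity correction and no dropout the total is 2504, within 3%. The figure is reproduced, but the 2424 evaluable patients are my inference and do not appear in the documents.

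**3. Equal misses in both arms (illustration for the future trial only).** Let a share m of true failures be handled in ways the definition does not count. The observed rates are 0.20(1 − m) and 0.15(1 − m), and the difference is 0.05(1 − m). Power is from the same pooled two-proportion test.

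| m (assumed) | Observed rates | Difference | Power, 1212 per arm | Power, 1276 per arm |
|---|---|---|---|---|
| 0 | 20% vs 15% | 5.0 points | 90.0% | 91.4% |
| 10% | 18% vs 13.5% | 4.5 points | 86.1% | 87.7% |
| 20% | 16% vs 12% | 4.0 points | 81.0% | 83.0% |

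The risk ratio stays at 0.75; only the absolute difference shrinks.

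**4. Unequal misses.** If 10% are missed in the standard-dose arm only, the rates are 18% vs 15% and the difference falls to 3.0 points. If 10% are missed in the high-dose arm only, they are 20% vs 13.5% and it rises to 6.5 points. The direction is therefore not fixed.

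**5. The pilot itself.** With 64 patients, about 32 per arm, expected failures are 32 × 0.20 = 6.4 and 32 × 0.15 = 4.8. The 95% half-width for the difference is 1.96·√(0.16/32 + 0.1275/32) = 0.186, about 19 points. One reclassified patient moves an arm's rate by 1/32, about 3 points.

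**The case against.** The strongest reply is that the omitted events may be rare. Section 1 describes intravenous treatment as the usual response to oral failure, and the definition counts that. The local specialists' preference for the higher dose, in the same section, is not stated as a response to worsening. No document gives an instance or a frequency of same-class rescue. This stands, and it is why no size can be assigned.

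A reader might infer that escalation would fall mainly on standard-dose patients, since 4 × 500 mg = 2 g daily lies below the top of the range in section 6.2 while 4 × 1000 mg = 4 g is at the top. On that reading 10% missed in that arm alone would cut full-trial power to about 51% (1212 per arm) or 53% (1276 per arm). The documents do not support this as the expected case. Physicians are blinded and no unblinding step is described, so they cannot direct increases to one arm. An open-label order for the higher dose would change the dose only for standard-dose patients, so some asymmetry is possible, but its extent is speculation.

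A reader might also infer that a lower pilot failure rate would feed into the size of the full trial. Appendix A uses 20%, section 1 attributes a rate of about that size to earlier studies, and nothing says that the pilot's rate will replace it. Nor can we see whether those studies counted same-class changes. If they did not, the 20% is already net of them, and the discount in the table would double-count.

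Finally, some capture may already exist. Day 3 response, Day 7 cure, 14-day return visits and the adherence outcome may reflect some of these patients, section 4.9 extracts treatment records, and the case record forms were filed separately. That weakens any claim that data are missing. It does not settle how the primary effectiveness outcome classifies these patients.

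**Conclusion.** The gap holds on the text: a patient who meets the worsening criteria and receives a same-class oral switch, a higher cephalexin dose or a longer course is a non-failure. It would go too far to say that such patients count as successes. The protocol has no such category, and secondary outcomes may show some of them as not responding or not cured.

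It would also go too far to say that the bias must run toward zero. Equal misses shrink the absolute difference, by 0.5 to 1.0 point if 10% to 20% of failures are missed; unequal misses could move it either way. Those shares are assumptions, and the power figures illustrate a future trial under an assumed alpha and allocation ratio.

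For the pilot, a shift of that size is small against a half-width of about 19 points, and the primary outcome is feasibility. This is a worthwhile, low-cost improvement and does not undermine the pilot. Its main value is that refining procedures is a stated aim in section 3, and the pilot is the place to learn whether these events are rare.

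**What to change.** Keep the current definition of failure, and add three things:

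- Record every antibiotic change made for worsening, by type: same-class switch, dose change, extension, addition. State how each is classified under the present definition.
- Pre-specify in section 4.12 a sensitivity analysis of the primary effectiveness outcome in which any such change within 7 days, after the worsening criteria are met, counts as failure.
- Report by arm the number of patients who met the worsening criteria, whatever was done with the antibiotic. These criteria are already assessed at Days 3 and 7, because meeting them triggers referral to the ED.

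The cost is a form field, if the separately filed forms do not already have one, one extra analysis, and a second failure count to report and explain. Existing visits and record extraction are enough. The change concerns only how outcomes are recorded and counted; no change to clinical management is proposed.

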4.12 Data Analysis

Baseline demographic and clinical characteristics of participants will be described using descriptive statistics. Primary and secondary feasibility outcomes will be described using frequency and proportion with two-side 90% confidence intervals. Primary and secondary effectiveness outcomes will be described using frequency and proportion in each arm, together with 95% confidence intervals for the difference between the two arms. Analysis will proceed according to an intention-to-treat protocol.

While every effort will be made to avoid attrition, the prevalence of any missing data will be described in each arm and multivariable regression analysis will be used to identify baseline characteristics associated with attrition. Any identified characteristics will need to be adjusted for in the primary and secondary outcome analyses to avoid bias due to attrition. Single or multiple imputation will be used as sensitivity analysis to explore the implications of non-randomly missing data under extreme assumptions about attrition.

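### Day 7 clinical cure is defined by signs alone, so a patient switched for worsening infection can be both a treatment failure and a cure, which can dilute the cure comparison but not the primary outcome

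*Combined protocol and SAP*

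**What the plan says.** Section 4.8.2 builds the primary effectiveness outcome on a treatment event. Failure is "defined as a change in antibiotic (change in class of oral antibiotic or step up to intravenous therapy) within 7 days", where the reason is worsening infection by fever, erythema or pain criteria.

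Two secondary outcomes in the same section are built on the patient's state on one day:

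- Day 7: "Clinical cure (no erythema, pain and fever) at day 7".
- Day 3: at least a 20% "reduction in area of erythema compared to baseline) at day 3".

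Neither mentions whether the antibiotic has been changed by then. Study assessments fall on Day 3 and Day 7. For patients who have worsened, the section says: "If criteria are met for worsening infection, they will be sent to the ED for evaluation". Section 1 describes what usually follows a failure: "patients are typically switched to intravenous therapy and may require hospitalization".

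Section 4.12 reports each effectiveness outcome as a proportion per arm with a 95% confidence interval for the difference. It adds: "Analysis will proceed according to an intention-to-treat protocol". It has rules for missing data but none for patients who switched.

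**The concern.** A patient who worsens, is found on Day 3 and is moved to another antibiotic has up to four days on that treatment before the Day 7 assessment. If the signs have gone by then, the definitions as written make this patient a failure and a cure, both attributed to the allocated cephalexin dose.

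Section 3 asks for preliminary evidence comparing the two doses. A recovery achieved on a different drug does not measure that. The arm with more failures also has more switched patients, so its cure proportion is raised more, and the cure comparison moves towards no difference.

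Because no handling rule is stated, two analysts could also report different cure rates from the same data, and the choice could be made after results are known. The pilot exists to refine procedures for a larger trial (sections 2, 3 and 5), so the definition may be carried forward.

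**Working it through.** **Inputs from the plan.** Failure is 20% on standard dose, with a minimum important difference of 5 points (Appendix A). The hypothesis is fewer failures on high dose (section 1), so 15% is used there. The target is 64 patients (4.11), randomized 1:1 (4.7), or 32 per arm.

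**The plan's own figure.** Appendix A gives 2552 patients in total for 90% power. It does not state alpha; I assume 0.05 two-sided. With mean proportion 0.175:

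- n per arm = [1.960·√(2·0.175·0.825) + 1.282·√(0.20·0.80 + 0.15·0.85)]² / 0.05² ≈ 1212, or 2424 in total.
- With continuity correction the total is 2504, which is 1.9% below 2552.
- 2424/0.95 gives 2552 exactly, but no 5% allowance is stated.

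This confirms 20% versus 15% as the working rates. The documents give no figure for cure or response.

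**Model.** Let f be the failure rate, c the Day 7 cure rate among non-failures and r the Day 7 cure rate among switched patients. Both c and r are assumed, and each is taken as equal in the two arms.

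- Cure on signs alone = (1 − f)·c + f·r. Arm difference = 0.05·(c − r).
- Cure with switched patients counted as not cured = (1 − f)·c. Arm difference = 0.05·c.
- Absolute shift = 0.05·r. Share of the failure-driven difference lost = r/c.

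**Results with c = 0.60**

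| Rule | Standard | High | Difference (points) | Share lost |
|---|---|---|---|---|
| Switched = not cured | 48.0% | 51.0% | 3.0 | – |
| Signs only, r = 0.10 | 50.0% | 52.5% | 2.5 | 17% |
| Signs only, r = 0.25 | 53.0% | 54.75% | 1.75 | 42% |
| Signs only, r = 0.50 | 58.0% | 58.5% | 0.5 | 83% |

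For c = 0.40 the 2.0-point difference becomes 1.5, 0.75 or −0.5. For c = 0.80 the 4.0-point difference becomes 3.5, 2.75 or 1.5. Nothing is lost at r = 0, and everything at r = c.

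**Patients in both categories.** Expected failures are 32·0.20 + 32·0.15 = 6.4 + 4.8 = 11.2. Multiplying by r gives about 1, 3 or 6 patients at r = 0.10, 0.25 or 0.50.

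**Against the pilot's precision.** The 95% half-width for a cure difference is about 1.96·√(2p(1 − p)/32), with p = 0.8c. It is 22.9, 24.5 and 23.5 points for c = 0.40, 0.60 and 0.80. The largest shift above is 2.5 points.

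**Day 3.** The first scheduled visit that refers patients to the ED is the Day 3 visit itself, so only an unscheduled switch before that visit can affect response. A patient whose erythema has grown by 20% or more at Day 3 cannot be a responder then. A patient who meets the fever or pain criterion can be, but a switch made after that visit comes after the response was measured.

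**The case against.** The strongest reply is that there is no contradiction to repair. Failure and cure answer different questions, and assessing signs regardless of a switch is a legitimate treatment-policy reading of intention-to-treat. The documents are silent on switched patients; they do not expressly count them as cured. This stands in part: the signs-only analysis is defensible if it is chosen and stated. The plan does not state it, and it fits the dose question of section 3 less well.

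A reader might infer that rescue hides the dose effect. The documents do not support that. The primary outcome is the switch itself and cannot be diluted by it. In the model above, the cure difference is only the 5-point failure difference multiplied by c, so the stricter definition recovers nothing that the primary outcome does not already show.

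A reader might also infer that the cure comparison would reverse. That needs r above c: patients who worsened would have to be cured more often than patients who never failed. Nothing in the documents suggests this. Complete absence of erythema, pain and fever within days of worsening is a demanding standard. A failure identified by worsening signs at the Day 7 visit cannot be a cure at that visit, which lowers the average r.

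Finally, these are descriptive secondary outcomes in a 64-patient pilot, and the full trial is sized on failure, not cure. That stands: no sample size is wrong on this account.

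**Conclusion.** The gap is real and modest. As written, sections 4.8.2 and 4.12 let one patient count as a failure and as a Day 7 cure for the allocated dose. The cure comparison can be diluted by the share r/c of its failure-driven part: 17% to 83% for c = 0.60 and r from 0.10 to 0.50, or 0.5 to 2.5 points. The size rests on c and r, which the documents do not give, and on both being equal across arms.

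It does not follow that the dose effect is masked, that the sign would change or that the pilot's conclusions would be overturned. The primary outcome is untouched, Day 3 exposure is limited to early unscheduled switches, and the shift is far inside the pilot's interval. What is at stake is how the cure figures are read and whether the definition goes forward. In a trial of 2552 (1276 per arm), the half-width at p = 0.48 would be 1.96·√(2·0.48·0.52/1276) ≈ 3.9 points, and a shift of 1 to 2.5 points would no longer be negligible.

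**What to change.** In section 4.8.2, define Day 7 cure and Day 3 response as the stated signs plus no change of antibiotic for worsening infection before that same assessment. Say explicitly that a failure after the Day 3 assessment does not alter Day 3 response. In section 4.12:

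- report the signs-only version of both outcomes as a supplementary row;
- cross-tabulate treatment failure by Day 7 cure in each arm;
- report switches for other reasons, such as intolerance, separately, since they are not failures but also affect what a cure means.

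The cost is one clause and a few table rows. The primary outcome already requires the change of antibiotic, its reason and its timing, so no new visit or data item should be needed.

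The downside is that reported cure falls in each arm by the failure rate times r. At c = 0.70 and r = 0.50, standard dose goes from 66% to 56% (0.20·0.50 = 10 points) and high dose from 67% to 59.5% (0.15·0.50 = 7.5 points). Keeping the signs-only row lets readers see both. The change concerns the outcome definition only, not clinical management.
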